- Response evaluations will be conducted every 8 weeks (after every 2 cycles). The window period is set at ±7 days.
- The administered dose may be rounded to one decimal place.
- The treatment will continue until the occurrence of any of the following events.
 - Disease progression
 - Occurrence of unacceptable adverse effects
 - Withdrawal of consent
- The end-of-treatment visit will be conducted on the day treatment is discontinued or within 30 days of the last administration.
- The survival status will be assessed every 8 weeks after the end-of-study visit, with a window period of ±2 weeks (assessment can be conducted via phone).

B. General principles for chemotherapy dose adjustment

- ① Dose reduction or treatment delay is planned for severe hematologic or non-hematologic adverse events occurring during clinical trial treatment. Dose adjustment should be performed based on the severity of the adverse event in the most severely affected organ system. Adverse events will be graded using NCI CTCAE version 5.0.
- ② If the subject experiences multiple adverse events with conflicting recommendations, the most conservative dose adjustment recommendation will be followed.
- ③ It should be noted that doses reduced due to adverse events cannot be re-escalated.
- ④ All adverse events must be resolved to Grade 1 or lower before resuming treatment. Dose adjustments should be based on the severity of the adverse event in the most severely affected organ system. Missed doses during the treatment cycle should not be made up.
- ⑤ If the investigator determines that an adverse event is unlikely to progress to a severe or life-threatening level (e.g., alopecia, taste alterations), treatment will continue at the same dose without dose reduction or interruption. Additionally, (non-hemolytic) anemia can be managed satisfactorily with transfusion, and therefore dose reduction or treatment interruption is not required in such cases.
- ⑥ Dose adjustments for a single abnormal hematologic laboratory value will be based

on hematologic parameters at the start of the treatment cycle. Since specimen collection is not scheduled during the treatment cycle, nadir level measurements will not be conducted.

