- ⑦ If recovery does not occur within a maximum of 3 weeks after the scheduled resumption of treatment, resulting in a delay in the treatment cycle, the protocol treatment will be discontinued unless both the investigator and the subject determine that continuing chemotherapy is the only viable option.
- ⑧ The dosing amount is based on baseline body weight, and recalculation of BSA and dose adjustment is required if there is a weight change of 10% or more. (If the institution has a chemotherapy prescription system, it may be appropriately adjusted in consultation with the principal investigator's institution.)

C. Chemotherapy dose adjustment

- Dose reductions for adverse events can be adjusted based on the recommendations below, in accordance with the institution's standard treatment guidelines and the investigator's discretion.

<Dose Levels>

	Dose levels	Dose	
Oxaliplatin	Full Dose	85 mg/m²	100%
	Dose level -1	68 mg/m ²	80 %
	Dose level -2	51 mg/m ²	60%
Irinotecan	Full Dose	150 mg/m²	100%
	Dose level -1	120 mg/m ²	80 %
	Dose level -2	90 mg/m ²	60%
5-fluorouracil	Full Dose	2400 mg/m²	100 %
	Dose level -1	1920 mg/m ²	80 %
	Dose level -2	1440 mg/m ²	60%
5-fluorouracil	Full Dose	400 mg/m²	100 %
	Dose level -1	320 mg/m ²	80 %
	Dose level -2	240 mg/m ²	60%
Leucovorin	No dose reduction		

< Dose adjustment for hematologic abnormalities>

The hematologic criteria (absolute neutrophil count and platelet count) can be adjusted based on the domestic approval conditions of the investigational drug, referring to the criteria below.

	1.0≤ANC<1.5 x10⁹/L 75K≤ PLT <100K	0.5≤ANC<1.0 x10⁹/L 50K≤ PLT < 75K	ANC< 0.5 x10⁹/L PLT < 50K
First event	No dose adjustment	Dose reduction by one level for all drugs (oxaliplatin, irinotecan, and 5-FU).	Dose reduction by one level for all drugs.
Second event	No dose adjustment	Dose reduction by two levels for oxaliplatin and irinotecan. Dose reduction by one level for 5-FU.	Dose reduction by two levels for all drugs.

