In cases where neurological toxicity, reversible posterior leukoencephalopathy syndrome, septic shock, disseminated intravascular coagulation, hemolytic uremic syndrome, QT interval prolongation, or rhabdomyolysis are suspected or occur, appropriate treatment should be

administered, and the patient should be referred to a relevant specialist. Based on the investigator's judgment, treatment may be resumed with dose adjustment according to the toxicity grade once recovery is achieved.

2) Control group setting and randomization method

The investigational product will be administered only to participants enrolled in this clinical trial in accordance with the procedures specified in the clinical trial protocol. Participants who withdraw from the trial will retain their participant number. A new participant number must always be assigned to new participants. All eligible participants must be registered prior to the initiation of treatment.

3) Administration/Dosage of investigational products, method of administration, combination therapy, and use of control drugs

The chemotherapy regimens to be used in this clinical trial are mFOLFOX and mFOLFIRI.

The methods of administration and schedules for the drugs are as follows:

A. mFOLFOX (Administered as a single regimen every 2weeks)

1) mFOLFOX
D1
Oxaliplatin 85mg/m ² over 2hr
Leucovorin 400mg/m ² over 2hr
Fluorouracil 400mg/m ²
FU 2400mg/m ² over 46hr

B. mFOLFOX/mFOLFIRI (Administered alternately every 2 weeks.)

1) mFOLFOX	2) mFOLFIRI
D1	D1
Oxaliplatin 85mg/m ² over 2hr	Irinotecan 150mg/m ² over 2hr
Leucovorin 400mg/m ² over 2hr	Leucovorin 100mg/m ² over 2hr
Fluorouracil 400mg/m ²	5FU 2400mg/m ² over 46hr

FU 2400mg/m ² over 46hr	
------------------------------------	--

- The treatment will continue to be repeated until disease progression occurs, treatment is no longer feasible due to toxicity, or the patient declines further therapy.

4) Observation parameters, clinical laboratory tests, and methods of assessment

<Clinical study tests and observation items, schedule >

- A. The screening procedures must be conducted within 14 days prior to the initiation of treatment. (Screening tests may be used as Day 1 Cycle 1 tests.) Evaluation timeline: Day -14 to Day -1 (before drug administration)
 - ① Informed Consent: A signed consent form in the designated format.
 - ② Vital Signs and Physical Measurements: Body temperature, blood pressure, heart rate, height, and weight.
 - ③ ECOG Performance Status

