 - ④ History of Biliary Tract Cancer: Initial histopathological diagnosis and prior treatment history for biliary tract cancer.
 - ⑤ Medical History: Comorbid conditions and ongoing treatment history.
 - ⑥ Physical Examination: Clinical examination.
 - ⑦ Tumor Evaluation (only for areas with lesions): CT (abdomen and pelvis CT, chest CT), chest X-ray, bone scan (if needed), PET-CT (if needed).
 - ⑧ Tumor evaluation must be conducted within 14 days prior to the initiation of treatment, and the same evaluation method must be used.
 - ⑨ Laboratory Tests
 - a. Hematologic Tests: Hemoglobin, hematocrit, WBC (including differential count), platelet count.
 - b. Biochemical Tests: Total bilirubin, γ -GTP (if needed), AST/ALT, alkaline phosphatase, total protein, albumin, serum creatinine, BUN, tumor markers (CA19-9, CEA), creatinine clearance (Ccr based on the MDRD calculation formula).
 - ⑩ Quality of Life Assessment: FACT-G7 questionnaire.

B. Evaluation parameters during drug administration period

- ① Vital signs and physical measurements
- ② Clinical laboratory tests
- ③ Hematologic tests (evaluated every cycle): Hemoglobin, hematocrit, WBC (including differential count), platelet count.
- ④ Blood biochemical tests (assessed per cycle): Total bilirubin, γ -GTP (if needed), AST/ALT, alkaline phosphatase, total protein, albumin, serum creatinine, BUN, tumor markers (CA19-9, CEA) (tumor markers are assessed at each response evaluation), creatinine clearance.
- ⑤ Radiological measurement of lesions (Tumor Evaluation: CT (abdomen, pelvis CT, chest CT) (and/or MRI), chest X-ray, bone scan (if needed), PET-CT (if needed)): Evaluations should be conducted using the same methods. Additional tests may be used if symptoms are present or if deemed necessary. Tumor evaluations are performed every 8 weeks, with a window period of +/- 1 week.
- ⑥ Clinical findings regarding adverse events
- ⑦ Quality of life assessment (FACT-G7) – performed at each response evaluation (to be done before the consultation, with a window period of +/- 2 weeks).

C. Conditions for discontinuation of the investigational drug administration

In the cases described below, the administration of the drug should be discontinued, and the reason must be documented in the case report form.

- ① Patients with obvious disease progression or those for whom treatment cannot be administered due to the condition.

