- C. Overall Survival - Defined as the time from the initiation of second-line chemotherapy to the occurrence of death from any cause, analyzed as the event.
- D. Treatment Response - Analyzed based on RECIST 1.1 criteria, including complete response (CR), partial response (PR), and disease progression (PD).
- E. Disease Progression - Confirm the date of the CT scan showing disease progression based on RECIST 1.1 criteria.
- F. Progression-Free Survival - Defined as the time from the initiation of second-line chemotherapy to the occurrence of either disease progression or death without prior progression, analyzed as the event.
- G. Toxicity - Toxicity will be assessed at every treatment cycle through medical history, physical examination, and blood tests, and will be recorded based on CTCAE version 5.0.

6) Uniqueness compared to existing treatments and studies

There are currently no proven effective treatments for advanced or recurrent biliary tract cancer that is unresponsive to first-line therapy. However, recent systemic reviews suggest that second-line chemotherapy may provide some benefit. This study aims to identify the most effective combination of chemotherapy regimens. While most previous studies on second-line therapy for biliary tract cancer have been phase ii trials with a single-arm design, this clinical trial is a randomized phase ii study. It is designed to evaluate the most promising chemotherapy regimens based on their effectiveness in other gastrointestinal cancers, particularly pancreatic cancer. The study design, including both experimental and control groups, adds significant value to the research.

7) Benefits and risks to study participants

- A. The drugs used in this study are already effectively utilized in other cancer types, and their side effects and risks are well-documented. Appropriate management of these adverse effects is feasible within clinical practice.
- B. Second-line chemotherapy is considered potentially effective for biliary tract cancer,

and it is currently administered in routine clinical practice when deemed appropriate for the patient. This study aims to determine which of the two most promising drug combinations is more effective. Patients enrolled in this study will not receive under-treatment or excessive treatment.

8) Criteria for discontinuation or withdrawal

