Efficacy analysis will be based on the evaluation of patient responses according to RECIST v1.1 response criteria. The effectiveness of the investigational drug will be measured in terms of overall response rate (ORR) with 95% confidence intervals. The best overall response (BOR) during the period from drug administration to either disease progression or study termination will be reported. Target and non-target lesion evaluations will follow RECIST v1.1 criteria and will be conducted every 6 weeks. If clinical disease progression is suspected, the evaluation will be performed immediately prior to the termination of the clinical trial. All lesion evaluations for each patient must maintain consistent imaging methods throughout the treatment period, including the use of CT scans and X-rays to ensure uniformity. Lesions smaller than 10 mm at baseline must be documented using spiral CT in the medical record and consistently evaluated throughout the clinical trial. Where clinically feasible, oral and intravenous contrast agents should be used consistently. Tumor measurements during the clinical trial should be performed by the same investigator or radiologist. Additionally, tumor evaluation personnel at each institution must be trained in RECIST standards through participation in prior multi-center

clinical studies. Overall survival (OS) and progression-free survival (PFS) from the start of investigational drug administration will be analyzed using the Kaplan-Meier method. Analyses of the time to disease progression or death will include all available follow-up information.

D. Safety data analysis

Adverse events will be documented according to NCI CTCAE version 5.0. Additional analyses will be conducted based on the severity of adverse events and their causal relationship to the investigational drug. Standard safety analysis will be performed, including details on dose adjustments, serious adverse events (e.g., hospitalizations), and early study withdrawals.

E. Quality of life assessment (QoL)

Quality of life will be assessed using QoL questionnaire scores (FACT-G7). If the data satisfy normality assumptions, a two-sample t-test will be performed; otherwise, the Mann-Whitney U test will be used.

10. Measures to ensure participant safety

1) Ethical conduct of the study

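### Response evaluation is timed as every 8 weeks, as every 2 cycles and as every 6 weeks; these do not agree, and one calendar schedule for both arms is needed

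*Protocol*

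**What the plan says.** The protocol times the tumor evaluation in three places.

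- Section 9. 1) A: "Response evaluations will be conducted every 8 weeks (after every 2 cycles"), followed by "The window period is set at ±7 days".
- Section 9. 4) B, item 5: "Tumor evaluations are performed every 8 weeks, with a window period of +/- 1 week". There is no cycle count here.
- Section 9. 11) C: "Target and non-target lesion evaluations will follow RECIST v1.1 criteria and will be conducted every 6 weeks".

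Four other statements bear on how these work in practice.

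- Section 9. 3) gives the dosing interval: "mFOLFOX (Administered as a single regimen every 2weeks") for control and "mFOLFOX/mFOLFIRI (Administered alternately every 2 weeks".) for the experimental arm. Each regimen is shown with a day 1 only. The protocol does not define a cycle length.
- Section 9. 1) B, item 7, ends protocol treatment, with an exception, "If recovery does not occur within a maximum of 3 weeks after the scheduled resumption of treatment". Holds of up to 3 weeks are therefore foreseen, and longer ones are possible.
- Section 9. 5) E dates progression by imaging: "Confirm the date of the CT scan showing disease progression based on RECIST 1.1 criteria".
- Section 9. 5) F counts PFS from the start of second-line chemotherapy.

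No sentence says which anchor governs when treatment is delayed.

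**The concern.** A scan date can be fixed by the calendar or by treatment given. Section 9. 1) A does both in one sentence and so treats 8 weeks and two cycles as the same thing. At the stated dosing interval they are not the same, and if cycles are read as longer, delays separate them.

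The choice matters because progression takes the date of the scan that shows it. A site that follows the calendar scans held and unheld patients alike. A site that counts cycles scans held patients later and records their progression later. The arms contain different drugs, and the background section itself reports a different toxicity profile for FOLFIRI, so holds may not be equally frequent. PFS and response timing are exposed, and so are FACT-G7 and tumor markers, which section 9. 4) B ties to each response evaluation. Sites in a multi-site trial could resolve the ambiguity differently.

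**Working it through.** **Inputs from the protocol.** Evaluation interval 8 weeks, or two cycles, window ±7 days (9. 1) A); 8 weeks ±1 week (9. 4) B); 6 weeks (9. 11) C); administration every 2 weeks (9. 3)); hold of up to 21 days (9. 1) B, item 7).

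**Step 1: the plan's own equation.** The calendar rule puts the first scan on day 8 × 7 = 56, window day 49 to 63. The cycle rule puts it on day 2 × (cycle length in days) + total delay. With no delay, the two match only if a cycle is 56 / 2 = 28 days. The only interval stated is 14 days, which gives 2 × 14 = day 28. So the equation of 8 weeks with two cycles is not reproduced from the stated interval.

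**Step 2: adding delay, under both readings of a cycle.**

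| Total delay (days) | Cycle = 2 weeks: 28 + delay | Cycle = 4 weeks (not stated): 56 + delay |
|---|---|---|
| 0 | 28, outside | 56, inside |
| 7 | 35, outside | 63, inside |
| 8 | 36, outside | 64, outside |
| 14 | 42, outside | 70, outside |
| 21 | 49, inside | 77, outside |
| 42 | 70, outside | 98, outside |

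On the 2-week reading the rules conflict before any delay occurs. On the 4-week reading they agree until total delay exceeds 7 days, and a single permitted hold can exceed that.

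**Step 3: the 6-week statement.** Six weeks is day 42. Giving it the same ±7 days (an assumption, since 9. 11) C states no window) yields day 35 to 49, which meets the 8-week window on day 49 only. For the second scan, day 84 ± 7 (77 to 91) and day 112 ± 7 (105 to 119) do not overlap. By week 24 the schedules give 24 / 6 = 4 and 24 / 8 = 3 scans.

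**Step 4: can the effect on PFS be sized?** Only by assumption, because the protocol gives no hold rates by arm. Assume equal true PFS in both arms, exponential, median 4.0 months (the background figure for FOLFOX; 4.0 × 30.4375 / 7 = 17.4 weeks), progression recorded at the next scan, and one arm scanned every 8 weeks. If every scan in the other arm is 1 to 3 weeks late, the simulated hazard ratio is about 0.90 to 0.95. If only some intervals are lengthened, it ranges from about 0.90 to 1.00, depending on the hold pattern. Simulation error is about 0.01 to 0.02.

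The recorded median can move the opposite way. With scans every 8 weeks, the share progressed by week 16 is 1 − 2^(−16/17.4) = 47%, so the recorded median is week 24. With scans every 9 weeks, the share by week 18 is 1 − 2^(−18/17.4) = 51%, so it is week 18. The arm scanned later then has the better hazard ratio and the shorter median.

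**The case against.** The strongest reply is that the calendar rule plainly governs. It stands in the main clause of 9. 1) A, its window is in days, and 9. 4) B, the section that schedules the tests, repeats it with no cycle count. On that reading scan dates do not depend on toxicity. Sections 9. 4) B and 9. 11) C also provide for extra tests on symptoms and for evaluation when clinical progression is suspected, which limits late detection. Section 9. 1) B, item 4, says missed doses are not made up, so an omitted dose need not lengthen a cycle.

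Much of this stands. Timing follows treatment only where a site acts on the bracket. It does not remove the point: the bracket is an instruction in the design section, nothing ranks it below the calendar, and item 7 of 9. 1) B expressly foresees delayed cycles. The 6-week statement conflicts with the calendar rule as well.

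A reader might infer that delays cause the conflict at any cycle length. The table in Step 2 shows otherwise. Days 70 and 77 after one hold of 2 or 3 weeks need a 4-week cycle; with 2-week cycles a 3-week hold brings the scan to day 49, inside the window. On the 4-week reading, total delay of 7 days or less is absorbed.

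**Conclusion.** The evaluation schedule contradicts itself and should be reconciled. At the stated 2-week interval, two cycles are 4 weeks against a stated 8; on an unstated 4-week cycle, total delay above 7 days breaks the agreement; and the statistics section gives a third interval, 6 weeks. These results rest on the protocol's own figures alone.

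The consequence is narrower. PFS and response timing can follow treatment delay only at sites that count cycles, and arms become non-comparable only if delays also differ between them. A reader might infer that PFS is biased in favour of the more toxic arm. The protocol does not support that: it gives no delay frequencies for either arm, and under the assumptions in Step 4 the hazard ratio and the recorded median can point in opposite directions. Neither direction nor size can be stated. The primary endpoint, 6-month OS, does not use scan dates and is unaffected. The change is worth making because it is cheap and closes a route to unequal assessment of a secondary endpoint.

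**What to change.** 1. In section 9. 1) A, delete the bracketed cycle count.
2. State one calendar schedule for both arms, counted from the same origin as PFS (the start of second-line chemotherapy under 9. 5) F), with ±7 days. Say that scans are not moved when an administration is delayed or omitted.
3. Use the same sentence in section 9. 4) B, item 5.
4. In section 9. 11) C, replace the 6-week interval with the same schedule, so that all three sections agree. If the 8-week interval given in the other two sections is kept, evaluations fall at weeks 8, 16, 24 and so on.

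The cost is a few sentences in an amendment, and at the 8-week interval no scans beyond those already scheduled in 9. 1) A and 9. 4) B. The downside is that, after a hold, some scans will not coincide with a treatment visit.

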- L. Patients who are eligible for targeted therapy, including FGFR inhibitors or IDH1 inhibitors. (eligible for patient who unable to use these targeted agents due to drug cost.)
- M. Patients with active CNS metastases and/or carcinomatous meningitis.
- N. Patients who meet contraindications for the investigational drugs as per domestic regulatory guidelines, including patients with infections, Interstitial pneumonitis or pulmonary fibrosis, Severe diarrhea, Chronic inflammatory bowel disease, Intestinal paralysis or obstruction, Functional impairment due to peripheral sensory neuropathy, Severe renal dysfunction.
- K. Patients deemed ineligible by the investigator for any other reason.

3) Target sample size and calculation basis

Assuming a 6-month survival rate of 50% for the mFOLFOX group and 75% for the

mFOLFOX/mFOLFIRI group, a total of 58 evaluable patients per group is required to achieve 80% power at a significance level of $p=0.05$.

Considering a 10% drop-out rate, 65 patients per group need to be randomized, resulting in a total of 130 patients for the study. The enrollment period is planned for 2 years, with 1 year of follow-up.

4) Plan for enrollment of participants

[figure not shown]
The study will recruit patients who are already receiving treatment, without utilizing a separate [Participant Recruitment Advertisement]. The principal investigator and co-investigators will ensure that potential participants are not excluded from this study based solely on race or socioeconomic status. Efforts will be made to include all eligible patients who meet the inclusion criteria, and potential participants will be fully informed about the purpose of the study. Recruitment will aim to ensure that the study population represents the overall population of biliary tract cancer patients treated at the study institution.

9. Methods

1) Specific research methods

A. Clinical trial design

- 2nd-line treatment, Phase II
- Alternating mFOLFOX / FOLFIRI

< Study design >

- Screening will be conducted between Day -14 and Day 0 (the day of randomization). Radiological assessments for tumor evaluation are valid up to 2 weeks prior to the start of the study (Day 1).
- The initiation criteria for each cycle of chemotherapy administration are ANC > 1.0 × 10⁹/L and platelets > 75 × 10⁹/L.
- The window period for chemotherapy administration visits is set at ±3 days.

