- ② Patients who experience clinically severe or persistent side effects that make continued administration difficult (if the next dose is delayed by more than 3 weeks).
- ③ Cases where clinically significant abnormal test results are observed (if the next dose is delayed by more than 3 weeks).
- ④ If the patient wishes to discontinue the treatment.
- ⑤ If the patient refuses to receive the drug administration.
- ⑥ If the patient passes away.
- ⑦ If follow-up observation is not possible.

- ⑧ If the clinical trial investigator deems it necessary for any other reason.

D. End-of-treatment assessment

- ① Vital signs, physical measurements: Height, weight
- ② Clinical laboratory tests
 - a. Hematologic tests: Hemoglobin, hematocrit, WBC (including differential count), platelet count.
 - b. Blood biochemical tests: Total bilirubin, γ -GTP, AST/ALT, alkaline phosphatase (ALP), total protein, albumin, serum creatinine, BUN, tumor markers (CA19-9, CEA), creatinine.
- ③ Radiological measurement of lesions (if needed)
- ④ Clinical findings regarding adverse reactions

E. Follow-up investigation

- ① Adverse events related to the investigational drug and the tumor will be followed up until recovery. The reasons for trial discontinuation and the date of discontinuation must be documented in the case report form for all patients. The investigator is recommended to ensure that all necessary tests and procedures are completed when a participant is excluded from the clinical trial.
- ② The follow-up period begins after the end-of-trial visit and is conducted every 8 weeks. During the follow-up period, the following evaluation variables will be recorded. (Medical record review and survival confirmation can be done by phone):
 - a. Duration until disease progression for patients who did not experience disease progression up to the end of investigational drug administration.
 - b. Third-line treatment (including start date): Additional cancer treatments if known (e.g., chemotherapy, immunotherapy, targeted therapy, radiotherapy, and surgery).
 - c. Confirmation of survival status.

5) Criteria for efficacy evaluation and evaluation methods

- A. Death - Confirm the patient's date of death.

- B. 6-month survival rate - The proportion of patients who are alive at 6 months from the initiation of second-line chemotherapy (analyzed using the survival function).

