Cases meeting the following criteria will result in discontinuation of drug administration, and the reason will be documented in the case report form (CRF).

- A. Definite disease progression or patients unable to continue treatment due to their condition.
- B. Patients experiencing severe or persistent adverse events that make continued administration clinically challenging (e.g., when the next treatment cycle is delayed by more than 3 weeks).
- C. Clinically significant abnormal laboratory findings (e.g., when the next treatment cycle is delayed by more than 3 weeks).
- D. Patients who wish to discontinue treatment.
- E. Patients who refuse further drug administration.
- F. Patients who have died.
- G. Patients who are unable to undergo follow-up.
- H. Any other case deemed necessary by the investigator.

9) Safety evaluation criteria, methods, and reporting for adverse events

Severe adverse events (SAEs) will be reported according to the regulations of each institution's IRB. Reports to the IRB will also be submitted to the primary investigator (PI) institution.

10) Data and Safety Monitoring Plan (DSMP)

- A. Monitoring Responsibility - The principal investigator at each institution.
- B. Reporting of Adverse Events and Non-Compliance - Reports will follow the internal regulations and schedule established by the institution's IRB. The PI will also be informed during IRB reporting.
- C. Monitoring is scheduled at the following milestones: upon the registration of the first participant at the institution, when 20% of participants are enrolled, and at

the conclusion of the study.

D. Safety Meetings - In the event of a significant safety issue, any investigator can request a meeting. Meetings must be held within one week of the request to address the issue.

11) Data analysis and statistical methods

A. Analysis population

1. Overall efficacy analysis will be performed on the ITT (intention-to-treat) population, defined as all randomized patients.
2. Safety analysis will include all patients who received treatment.

B. Primary analysis

The primary analysis will measure the 6-month overall survival rate (OS rate) using the Kaplan-Meier method.

C. Secondary analysis

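### Survival endpoints are timed from the start of chemotherapy, yet efficacy is to be analysed in all randomized patients, so a patient who never starts has no time zero

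*Protocol*

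**What the plan says.** **Clock.** Section 9, item 5.B, defines the 6-month survival rate as "The proportion of patients who are alive at 6 months from the initiation of second-line chemotherapy". Item 5.C gives OS as "Defined as the time from the initiation of second-line chemotherapy to the occurrence of death from any cause", and item 5.F gives PFS as "Defined as the time from the initiation of second-line chemotherapy to the occurrence of either disease progression or death without prior progression". The statistical section (item 11.C) repeats the choice: "Overall survival (OS) and progression-free survival (PFS) from the start of investigational drug administration" are to be estimated by Kaplan-Meier.

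**Population.** Item 11.A states: "Overall efficacy analysis will be performed on the ITT (intention-to-treat) population, defined as all randomized patients". The next line sets a different population for safety: "Safety analysis will include all patients who received treatment". Item 11.B names Kaplan-Meier for the primary 6-month rate and mentions no exception to the efficacy population.

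**Timing.** Item 1.A says "Screening will be conducted between Day -14 and Day 0 (the day of randomization"), and treats Day 1 as the start of the study. Item 4.A says "The screening procedures must be conducted within 14 days prior to the initiation of treatment". Item 2 requires registration before treatment begins. No maximum interval from randomization to first dose is stated.

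**The concern.** Randomization comes before treatment, and the protocol separates the randomized set from the treated set. A patient can therefore be randomized and then refuse, deteriorate or die before the first dose. That patient must be in the efficacy analysis but has no origin from which to measure survival. Kaplan-Meier cannot place a patient without an origin, and no fallback date is given.

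If such patients drop out of the estimate, the arms are compared on a subset defined after randomization, and the primary analysis is no longer intention-to-treat. This biases the comparison only if two conditions hold together: non-starters differ between arms in number or prognosis, and their survival differs from that of starters. Deaths between randomization and first dose would also go uncounted.

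**Working it through.** **1. The statements side by side**

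| Item in section 9 | What it fixes | Setting |
|---|---|---|
| 5.B, 5.C, 5.F | Time zero for 6-month rate, OS, PFS | Start of second-line chemotherapy |
| 11.C | Time zero for OS, PFS | Start of study drug |
| 11.A, first line | Efficacy population | All randomized |
| 11.A, second line | Safety population | Treated only |

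All four endpoint statements start the clock at treatment, so this is not a slip in one place. For a patient in the efficacy population who never starts, time zero is undefined.

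**2. Whether follow-up closes the gap.** Survival status is checked every 8 weeks after an end-of-study visit (item 1.A; item 4.E calls it the end-of-trial visit). The only end visit with a stated time is the end-of-treatment visit, set by discontinuation or last administration. Follow-up of a non-starter is therefore not clearly provided for. Even if it were, it would give a death date and not a start date.

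**3. The plan's own sample size.** Section 8, item 3, gives 50% versus 75%, 80% power and a 0.05 level, without saying whether one- or two-sided. The two-sided two-proportion formula without continuity correction gives

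n = [1.960 × √(2 × 0.625 × 0.375) + 0.842 × √(0.25 + 0.1875)]² / 0.25² = 57.7, so 58 per arm.

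Then 58 / 0.90 = 64.4, so 65 per arm. Both stated figures reproduce. Power is 84.6% with 65 per arm analysed and still 80.2% if 7 per arm are lost. The issue is bias and loss of the randomized comparison, not power.

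**4. Size of the bias if non-starters are left out.** From the protocol: 65 per arm and the 50% control rate. Assumed, because the protocol gives no figure: the number k of non-starters, their 6-month survival s, a true rate p of 50% in both arms, and a two-sided 5% two-proportion test.

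Rate among starters = (p − f·s) / (1 − f), with f = k/65.

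Example with s = 0 and 3 versus 1 non-starters:
- k = 3: 0.50 / (62/65) = 0.524
- k = 1: 0.50 / (64/65) = 0.508
- Gap = 1.6 points. With n = 62 and 64, the standard error is about 8.9 points and the chance of rejecting is 5.4%.

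| Non-starters | s | False gap (points) | Type I error |
|---|---|---|---|
| 1 vs 0 | 0 | 0.8 | 5.1% |
| 3 vs 1 | 0 | 1.6 | 5.4% |
| 6 vs 3 | 0 | 2.7 | 6.0% |
| 6.5 (10%) vs 0 | 0 | 5.6 | 9.5% |
| 1 vs 0 | 0.30 | 0.3 | 5.0% |
| 3 vs 1 | 0.30 | 0.7 | 5.1% |
| 6 vs 3 | 0.30 | 1.1 | 5.2% |
| any | 0.50 | 0 | 5.0% |

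The errors use the unpooled variance. A pooled variance gives 9.4% in the 10% versus 0 row and the same figures to one decimal elsewhere.

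**5. Deaths before the first dose.** Assume a constant hazard giving 50% survival at 6 months: λ = ln 2 / 182.6 = 0.0038 per day. Expected deaths per arm over a gap of g days = 65 × (1 − exp(−λg)):
- g = 1: 0.25
- g = 7: 1.7
- g = 14, if every patient waited that long: 3.4

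**The case against.** The strongest reply is that the protocol excludes nobody. It expressly requires all randomized patients, so non-starters must be in, and all that is missing is a date. A separate analysis plan, if one exists, could supply it in advance. This stands in part. The protocol does not say that non-starters are dropped, and it cannot be assumed that their handling would be settled only after the data are seen. But an analysis plan that starts their clock at randomization would depart from the endpoint definition written in the protocol, and would mix two origins in one curve.

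A second reply is that items 5.B, 5.C and 5.F refer to second-line chemotherapy, not study drug, so a patient treated off study after refusing the allocated arm would still have a time zero. Item 11.C equates the start with study drug for OS and PFS. Even on the wider reading, patients who receive no second-line chemotherapy remain undefined.

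A third reply is that the listed reasons for discontinuation (refusal, inability to be treated, death) could be read to cover non-starters, and that item 4.E asks for the date and reason of trial discontinuation for every patient. That is a fair reading on data collection, but it provides no time zero.

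The reply on size stands. Randomization is Day 0 and Day 1 follows, so the gap should be short. mFOLFOX is listed first in the alternating arm, so cycle 1 may be the same in both arms. Pre-dose deaths that are equal between arms create no gap. A type I error of 6.0% needs 6 versus 3 non-starters, all dead by 6 months.

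**Conclusion.** The concern holds. The protocol fixes time zero at treatment start and the efficacy population at randomization, and for a patient who never starts the two cannot both be applied. This affects the primary endpoint as well as OS and PFS.

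The likely effect is small: under the assumed 1 versus 0 or 3 versus 1 non-starters, a false gap of 0.3 to 1.6 points against a design difference of 25 points, with type I error between 5.0% and 5.4%. It reaches 5.6 points and 9.5% only in the extreme case of 10% non-starters in one arm, none in the other, and all of them dead by 6 months. All these figures rest on assumed non-start counts and survival, and on the assumption that non-starters are left out. The case for correcting it is that the conflict is certain, it touches the primary analysis, and the remedy is cheap.

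**What to change.** - In section 9, items 5.B, 5.C, 5.F and 11.C, define the 6-month OS rate, OS and PFS from the date of randomization, for all randomized patients in their assigned arm, whether or not treatment starts.
- Add one line stating that survival status is also collected every 8 weeks for patients who never start.
- Keep timing from first dose only for safety summaries or as a sensitivity analysis.

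**Cost.** Four wording changes and one added line. The case report form must record the randomization date. Reported times lengthen by the short gap between randomization and first dose, and rates may look slightly less favourable because non-starters and pre-dose deaths now count. The targets of 58 evaluable and 65 randomized per arm are unchanged.
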